## 14.4 Publication, Disclosure, and Clinical Trial Registration Policy

## 14.4.1 Publication and Disclosure

The investigator is obliged to provide the sponsor with complete test results and all data derived by the investigator from the study. During the study, only the sponsor may make study information available to other study investigators or to regulatory agencies, except as required by law or regulation. Except as otherwise allowable in the clinical study site agreement, any public disclosure (including publicly accessible websites) related to the protocol or study results, other than study recruitment materials and/or advertisements, is the sole responsibility of the sponsor.

The sponsor may publish any data and information from the study (including data and information generated by the investigator) without the consent of the investigator. Manuscript authorship for any peer-reviewed publication will appropriately reflect contributions to the production and review of the document. All publications and presentations must be prepared in accordance with this section and the Master Services Agreement or equivalent agreement. In the event of any discrepancy between the protocol and the Master Services Agreement or equivalent agreement or equivalent agreement the Master Services Agreement or equivalent agreement will prevail.

IKERVIS®	
Study NVG16E128	Page 66 of 93
Protocol Version 4.0	23 March 2018

## 14.4.2 Clinical Trial Registration

In order to ensure that information on clinical trials reaches the public in a timely manner and to comply with applicable law, regulation and guidance, Santen will, at a minimum, register all clinical trials conducted in patients that it sponsors anywhere in the world on ClinicalTrials.gov or other publicly accessible websites before trial initiation.

## 14.4.3 Clinical Trial Results Disclosure

Santen will minimally post the results of clinical trials conducted in patients, regardless of outcome, on ClinicalTrials.gov or other publicly accessible websites, as required by applicable laws and/or regulations.

## 14.5 Insurance and Compensation for Injury

Each patient in the study must be insured in accordance with the regulations applicable to the site where the patient is participating. If a local underwriter is required, then the sponsor or sponsor's designee will obtain clinical study insurance against the risk of injury to clinical study patients. Refer to the Master Services Agreement or equivalent agreement regarding the sponsor's policy on patient compensation and treatment for injury. If the investigator has questions regarding this policy, he or she should contact the sponsor or sponsor's designee.

IKERVIS®	
Study NVG16E128	Page 67 of 93
Protocol Version 4.0	23 March 2018

## Appendix A Schedule of Study Procedures and Procedures

## Appendix A-I Schedule of Study Procedures

	Wash out period	Vash out period Open-label study treatment Period				
Study procedures	Screening Day $-14 \pm 3$	Baseline Day 1	Month 1 Day 28 ± 3	Month 2 Day 56 ± 3	Month 3 Day 84 ± 7	premature study discontinuation
Informed consent	Х					
Demographic information	Х					
Ocular and systemic medical history	Х	Х				
Previous and Concomitant ocular and systemic medications (incl. concomitant artificial tear usage)	Х	Х	X	Х	Х	$X^4$
Inclusion/exclusion criteria	Х	Х				
Efficacy Assessments						
Tear break up time (TBUT)	Х	Х	Х	Х	Х	$X^4$
Corneal fluorescein staining (Modified Oxford Scale)	Х	Х	X	Х	Х	$X^4$
Schirmer test (without anaesthesia)		Х			Х	$X^4$
Functional visual acuity (FVA parameters, FVA system)	Х	Х	X	Х	Х	$X^4$
Objective scatter index (OSI) (double-pass aberrometer)	Х	Х	X	Х	Х	$X^4$
RMS/Higher-order aberrations (Hartmann-Schack aberrometer)	Х				Х	X 
Investigator global evaluation					Х	X 

#### IKERVIS® Study No. NVG16E128 **Protocol Version 4.0**

	Wash out period		Unscheduled Visit /			
Study procedures	Screening Day $-14 \pm 3$	Baseline Day 1	Month 1 Day 28 ± 3	Month 2 Day 56 ± 3	Month 3 Day 84 ± 7	premature study discontinuation
Patient global evaluation					X	$X^4$
Visual Analog Scale (VAS) (photophobia, blurred vision)	$\mathbf{X}^1$	$X^1$	$\mathbf{X}^1$	$X^1$	X 	X 
Safety Evaluations						
Slit lamp examination	Х	Х	Х	Х	X	$X^4$
Uncorrected distance visual acuity (UDVA in LogMAR)	Х	Х	Х	Х	Х	$X^4$
Best corrected distance visual acuity (BCDVA in LogMAR)	Х	Х	Х	Х	X	$X^4$
Dilated fundus examination		Х			X	$X^4$
Intraocular Pressure (IOP)		Х			X	$X^4$
Urine pregnancy test (women of childbearing potential only)	Х	X 			Х	X 
Confirm patient discontinued treatment related to dry eye	Х					
Adverse events (AEs)		Х	X	Х	X	X 
Treatment Procedures						
Dispense study medication and unpreserved artificial tears	$X^2$	$X^2$	X 	X 		
Collection of used study medication and unpreserved artificial tears		X	X	X	X	X 

Footnotes are on last table page. ET/EOT=early termination/end of treatment. 1 VASs should be performed at the beginning of the visit before medical history and any study assessment see visit schedule section 9.3. 2 Dispense unpreserved artificial tears. Instruction: to be instilled up to eight times per day in each eye 3 Only for patients fulfilling criteria for severe keratitis that will be included. 4 Assessments to be performed during unscheduled visits only in case of premature discontinuation
IKERVIS®	
Study No. NVG16E128	Page 72 of 93
Protocol Version 4.0	23 March 2018

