## 9.3.2 Treatment Phase

All assessments should be done in the mentioned order to ensure that additional product doesn't interfere for the other result examinations.

## 9.3.2.1 Baseline: Day 1

- Inclusion/exclusion criteria review.
- Record Ocular and systemic medical history.
- Review of concomitant ocular and systemic concomitant medications (including artificial tear usage).
- Record adverse events (AEs)
- 0-100% VAS for photophobia and blurred vision severity
- UDVA
- BCDVA
- FVA parameters using FVA measurement system
- OSI using double-pass aberrometry system
- Slit lamp examination
- Dilated fundus examination
- TBUT

- CFS (modified Oxford scale)
- IOP
- Schirmer test (without anaesthesia)
- Urine pregnancy test (women of childbearing potential only)
- Collection of unpreserved artificial tear bottles (used/not used)
- Verify inclusion and exclusion criteria based on evaluations just performed:
  - Patients **fulfilling** the inclusion / exclusion criteria will receive the study treatment for the next month
  - Patients **not fulfilling** the inclusion / exclusion criteria will be discontinued from the study and the patient become screen failure (refer to section 9.1.9)
- Dispense study medication and unpreserved artificial tears for a 1-month period. Patients will be instructed on dosing of study medication.
- Patients will be scheduled to return to the clinic in 28 days  $\pm$  3 days for Month 1 visit.

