9.3.2.2 Month 1: Day 28 ±3 days

- Record concomitant ocular and systemic concomitant medications (including artificial tear usage)
- Record adverse events (AEs)
- 0-100% VAS for photophobia and blurred vision severity
- UDVA
- BCDVA
- FVA parameters using FVA measurement system
- OSI using double-pass aberrometry system
- Slit lamp examination
- TBUT
- Corneal fluorescein staining (modified Oxford scale)
- Collection of used/not used study medication containers and unpreserved artificial tear bottles
- Dispense study medication and unpreserved artificial tears for a 1-month period (Month 1 Month 2)
- Patients will be scheduled to return to the clinic on Day  $56\pm3$  days for Month 2 visit.

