9.3.2.4 Month 3: Day 84 ±7 days

- Record concomitant ocular and systemic concomitant medications (including artificial tear usage)
- Record adverse events (AEs)
- Patient global evaluation of efficacy
- 0-100% VAS for photophobia and blurred vision severity
- UDVA
- BCDVA
- FVA parameters using FVA measurement system
- OSI using double-pass aberrometry system
- RMS of higher order aberrations using Hartmann-Shack aberrometer
- Slit lamp examination
- Dilated fundus examination

- TBUT
- CFS including assessment of complete corneal clearing (modified Oxford scale)
- IOP
- Schirmer test (without anaesthesia)
- Investigator global evaluation of efficacy
- Urine pregnancy test (women of childbearing potential only)
- Collection of study medication containers used/not used study medication containers and unpreserved artificial tear bottles.

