## 9.3.4.5 Patient Global Evaluation of Efficacy

Patient will conduct an overall assessment of the effect of the study medication using the following rating scale:

- (3) = Very satisfactory.
- (2) = Satisfactory.

.....

- (1) = Not very satisfactory.
- (0) =Unsatisfactory.

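### The schedule footnote puts the symptom VAS first at every visit, but the ordered visit lists put it later and, at Month 3 and early termination, directly after the patient has rated the drug's efficacy

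*Protocol*

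**What the plan says.** Two instructions govern when the VAS is done.

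- **Schedule footnote.** In Appendix A-I, footnote 1 is attached to the VAS at Screening, Baseline, Months 1 to 3 and the premature discontinuation visit. It reads "VASs should be performed at the beginning of the visit before medical history and any study assessment" and then refers the reader to Section 9.3. SAP Table 1 carries the same rule without the cross-reference.
- **Visit lists.** Section 9.3.2 introduces the treatment-phase lists with "All assessments should be done in the mentioned order to ensure that additional product doesn't interfere for the other result examinations". Sections 9.3.2.1 to 9.3.2.4 then place the VAS after other items. At Baseline these include "Record Ocular and systemic medical history". At Month 3 the item immediately before the VAS is "Patient global evaluation of efficacy".

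Section 9.3.4.5 describes that item: "Patient will conduct an overall assessment of the effect of the study medication using the following rating scale", with four grades from unsatisfactory to very satisfactory. Appendix A-I lists it among the efficacy assessments, at Month 3 and premature discontinuation only. Section 9.3.3 requires the Month 3 examinations when a patient stops early at an unscheduled visit.

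Change from baseline in the two VAS scores is a secondary efficacy endpoint (protocol Section 5.2.2.1, SAP Section 2.2.2.1).

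**The concern.** The footnote shows that the sponsor wanted symptoms scored before any other questioning. The lists undo this, and the footnote does not settle the matter because it sends the reader to the section that conflicts with it. With up to four sites, different sites may resolve the conflict differently.

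Month 3 is where it matters most. Blurred vision and photophobia are the only symptom scores that patients give in this study. A patient who has just said how satisfactory the drug was may mark the scales in line with that answer. The study is open-label with one arm, so the patient knows the treatment and no comparator shares the same sequence. The Baseline VAS has no efficacy rating before it, so an effect at Month 3 would stay in the change score.

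**Working it through.** No formula in the plan applies, and the plan gives no figure to reproduce. The check sets the texts side by side and then traces which outputs use the Month 3 VAS.

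**Step 1. Position of the VAS.** Footnote 1 requires 1st place throughout.

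| Visit (protocol section) | Items listed before the VAS | VAS position | Efficacy rating before the VAS? |
|---|---|---|---|
| Baseline (9.3.2.1) | criteria review, medical history, medications, AEs | 5th | No |
| Month 1 (9.3.2.2) | medications, AEs | 3rd | No |
| Month 2 (9.3.2.3) | medications, AEs | 3rd | No |
| Month 3 (9.3.2.4) | medications, AEs, patient global evaluation | 4th | Yes |
| Early termination (9.3.3) | no list of its own; Month 3 examinations repeated | as Month 3 | Yes, if the Month 3 order is used |

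The Screening list (9.3.1.1) also puts the VAS after the history and medication items, but the sentence on order stands under 9.3.2 and does not formally cover Screening. Among the lists it does cover, medical history precedes the VAS at Baseline only.

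**Step 2. Can both rules be followed?** No. The global evaluation is a study assessment by the schedule's own grouping, so the footnote places it after the VAS, while the Month 3 list places it before.

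**Step 3. What an order effect would do to the change score.** Let d be the shift in a patient's Month 3 VAS caused by the preceding rating. The observed change is (Month 3 VAS + d) − Baseline VAS, that is, the true change + d. No such term arises at Baseline, so d does not cancel. The mean change moves by the mean of d.

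**Step 4. Which SAP outputs use Month 3 VAS change.**
- Section 8.2.1: descriptive summaries for 2 symptoms, giving 2.
- Section 8.2.3.1: same-visit Spearman correlations of CFS and of LogMAR FVA with each symptom, 2 × 2 = 4.
- Section 8.2.3.2: lagged Spearman correlations of CFS at Month 1 or Month 2 with each symptom at Month 3, 2 × 2 = 4. The lagged VAS pairs are with CFS only; LogMAR FVA has none.

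The total is 2 + 4 + 4 = 10.

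**Step 5. Which of these a shift could alter.** If d is the same for every patient, the ranks of the changes are unchanged, and so are the 8 Spearman coefficients, apart from truncation at 0% or 100%. Only the 2 descriptive summaries move. The correlations are affected only if d differs between patients.

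**Step 6. Primary endpoints.** These use changes in CFS, VMR and variance of OSI (protocol Section 5.2.1). None involves the VAS.

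**The case against.** The strongest reply is that a sensible site would not be misled. Both instructions say should, so neither is strictly mandatory. The stated reason for the listed order is that instilled products should not disturb later examinations, and a questionnaire instils nothing. Doing the VAS first and then following the list honours the footnote and defeats no stated purpose. The footnote is also the more specific instruction, and the SAP repeats it. Nor are the lists reliable on order elsewhere: they put IOP before the Schirmer test, while Section 9.3.5.5 puts IOP after the other dry eye assessments.

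This shows that the conflict is easy to resolve and that priming occurs only at sites that followed the lists. It does not remove the conflict. Section 9.3.2 is the text that presents itself as the working order, and nothing tells a site which instruction prevails.

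A second reply is that little depends on the VAS. It is secondary, and the SAP calls the study exploratory (Section 6.4) and plans no formal hypothesis testing (Section 8). That stands, and it sets the weight of the point.

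**Conclusion.** The contradiction is real and unresolved in the current protocol, and the SAP repeats the footnote's side of it. Its consequence is an avoidable order asymmetry in a secondary patient-reported endpoint at Month 3 and early termination. It is minor.

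The conclusion rests on two assumptions: that some sites follow the listed order, and that a global efficacy rating can influence symptom marks made directly afterwards. The documents confirm neither.

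A reader might infer more, but the documents do not support it:

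- **That Month 3 symptom change is biased in the drug's favour.** There are no data on the size or direction of an order effect, and dissatisfied patients could shift the other way.
- **That the effect can be sized against the supportive trial's −12.82 change in ocular discomfort VAS (Section 4.1.3).** That is a double-masked Month 6 result on a different score, and the documents give no order-effect size to set against it.
- **That the VAS correlations are distorted.** A uniform shift leaves Spearman ranks essentially unchanged.
- **That the earlier position of medication and AE questions at Months 1 and 2 causes bias.** It departs from the footnote, but no comparable mechanism is evident.

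**What to change.** - In protocol Sections 9.3.2.1 to 9.3.2.4, list the VAS as the first item. In Section 9.3.1.1, list it directly after consent. This brings the lists into line with footnote 1 of Appendix A-I and SAP Table 1.
- At Month 3, place the Patient Global Evaluation of Efficacy after the VAS, and state in Section 9.3.3 that the same order holds at early termination.
- For data already collected, establish and report the order each site used, or say that it is not known, and read the Month 3 and early-termination VAS changes in that light. The SAP reports that 17 patients were enrolled (Section 3.1), so reordering the lists may change few or no data here.
- Correct the lists before reusing them in the phase IIIb study foreseen in protocol Section 4.2, which is aimed at symptoms.

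The cost is a reordering of list items and a sentence in the report. No assessment or visit time is added.

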## Appendix A-II Visual Analog Scale (VAS) – Symptoms of Ocular Discomfort

The patient will be asked to assess each symptom regarding ocular discomfort unrelated to instillation among a list of 2 symptoms, i.e., blurred vision and photophobia. The patient will be asked to rate each ocular symptom of each eye by placing a vertical mark on the horizontal line to indicate the level of discomfort. 0% corresponds to "no discomfort" and 100% corresponds to "maximal discomfort."

Blurred Vision	0%	50%	100%
Photophobia	0% 	50%	100%

The response will be measured in % between 0 - 100%.

## Appendix A-III Best Corrected Distance Visual Acuity Procedure in LogMAR

The distance visual acuity test should be done with the best correction. The investigator will use the same chart for both eyes throughout the study.

#### Equipment:

An ETDRS or modified ETDRS chart may be used.

If a Lighthouse chart is used (dimensions  $62 \ge 65 \text{ cm} / 24.5 \ge 25.5$  inches), the patient must be seated at 4 meters (13 feet) from the chart. If a smaller reproduction is used (dimensions  $45.5 \ge 45.5 \text{ cm} / 18 \ge 18$  inches), the patient must be seated at 3 meters (10 feet) from the chart.

The same lighting conditions must be used throughout the course of the study.

### Procedure:

The patient should be seated in front of the chart.

The right eye must be tested first and the left eye must be covered. The patient should try to read each letter, from left to right, beginning at the top of the chart. The patient must be told that the chart contain only letters and no numbers. The patient must read slowly (about one letter per second). The investigator should not point on the chart during the test, but he must push /motivate the patient to read as far as he can during the test. The test is stopped when the patient cannot read any correct letter on the chart with the right eye.

During the test, the investigator must count all the missed letters (=errors):

- If the patient changes his response after reading the next letter, the change is regarded as an error.
- If the patient cannot read one letter, this is regarded as an error too.

Please note that if the patient changes his response before reading the next letter, this change is not regarded as an error.

The same procedure must be repeated with the left eye.

LogMAR calculation:

The investigator must calculate the score as follows:

LogMAR Visual acuity = baseline value + (N x 0.02)

With:

- Baseline value: this is the lowest line where the patient can read at least one correct letter
- N: this is the total number of missed letters (letters read incorrectly or letters not read up to the last/baseline line)
- 0.02 is the value for each letter

### Example:

If a patient misses 3 letters of 5 at the 0.2 LogMAR line and 4 letters of 5 at the line 0.1 (lowest line where the patient can read at least one correct letter), the calculation is:

- Last line read = 0.1 = baseline value

$$N = 4 + 3 = 7$$

Then score =  $0.1 + (7 \times 0.02) = 0.24 \text{ LogMAR}$ 

If a patient misses 2 letters of 5 at the 0.0 LogMAR line and 3 letters of 5 at the line -0.1 (lowest line where the patient can read at least one correct letter), the calculation is:

- Last line read = -0.1 = baseline value

- 
$$N = 2 + 3 = 5$$

Then score =  $-0.1 + (5 \times 0.02) = 0.0 \text{ LogMAR}$ 

## Appendix A-IV Functional Visual Acuity (Kaido 2013).

The functional visual acuity (FVA) will be measured using FVA measurement system (AS-28; Kowa, Aichi, Japan) at each study visit. The changes with time in the continuous visual acuity using the Landolt optotypes (Figure 2) with their sizes change depending on the correctness of the responses.

The optotypes are displayed automatically, starting with smaller ones. When the response is correct, even smaller optotypes are presented. If the responses are incorrect, larger optotypes are presented automatically (Figure 3). Visual acuity is continuously measured from the baseline best corrected Landolt visual acuity. The functional visual acuity measurement system can measure visual acuity from 150/100 to 20/200. When there is no response within the set display time, the answer is assumed to be an error, and the optotype enlarged automatically.

The outcomes will be recorded as starting visual acuity, LogMAR functional visual acuity, visual maintenance ratio, and maximal and minimal visual acuities:

- Starting visual acuity is defined as the baseline visual acuity, which is the value of the standard best corrected visual acuity measured by the functional visual acuity measurement system
- Functional visual acuity is defined as the mean value of time-wise change of the visual acuity during the overall examination
- Visual maintenance ratio (VRM) is calculated as follows (Kaido 2006, Kaido 2011):

visual maintenance ratio = (lowest LogMAR visual acuity score –functional visual acuity

at 60 s)/(lowest LogMAR visual acuity score – baseline visual acuity)

An increase in VMR from baseline will indicate an improvement.

• Maximal and minimal visual acuities are defined as the highest and lowest visual acuities recorded during the examination.

**Figure 2** Presentation of Landolt optotypes on mini-pointer of the functional visual acuity device (Kaido 2013).

Figure 3 flowchart diagram of optotypes during functional visual acuity testing (Kaido 2013).

## Appendix A-V Objective Scatter Index (Habay et al 2014)

Objective Scatter Index (OSI) and its variance will be measured using double-pass aberrometer at each study visit.

The system is driven by a software allowing a dynamic measure of the Point Spread Function (PSF) over 20 seconds with a resolution of half a second. For each PSF measure, the OSI is calculated, corresponding to the ratio of the light recorded in a ring area of 12 to 20 minutes of arc, and a circular area of 1 minute of arc.

Before proceeding to the test, the patient closes his/her eyes for 10 sec, then blinks 5 times to obtain the most homogenous spreading of the lachrymal film on the cornea surface.

Each measure is to be performed once. When measurement is to be performed on both eyes in the same patients, results will be considered as independent.

A decrease in OSI variance from baseline will indicate improvement.

## Appendix A-VI Higher Order Aberrations

Serial measurements of ocular higher-order aberrations are performed by means of Hartmann-Shack wavefront aberrometer.

Higher-order aberrations will be measured during a blink-free period of 20 seconds without instillation of topical anesthesia.

The higher-order aberration data will be analysed quantitatively for the central 4-mm-diameter zone up to the fourth order by expanding the set of Zernike polynomials. From the Zernike coefficients, the root mean square (RMS) will be calculated to represent the wavefront aberrations. The third-order Zernike coefficients (coma-like aberrations, S3), fourth-order Zernike coefficients (spherical-like aberrations, S4), and total higher-order aberrations (S3 + S4) will be calculated.

